8.2.3.4. Subgroup analysis

Number and proportion of patients with at least one adverse reaction will be tabulated by factor specified in Section 5.4. Tests specified in Section 8.1.3 will be performed to evaluate the relationship between patient demographics, etc. and development of adverse reactions. Furthermore, risk ratio and risk difference for the incidence of adverse reactions and their 95% confidence intervals will be calculated between subgroups.

In addition, number and proportion of patients with adverse reactions in each subgroup will be tabulated by SOC and PT for factors showing a significant difference by testing to evaluate the relationship between patient demographics, etc. and development of adverse reactions. Moreover, patient demographics, etc. (including breakdown of past medical history and complications, prior and concomitant medications) will be tabulated in each subgroup and number and proportion of patients with serious adverse reactions will be tabulated by SOC and PT in each subgroup as necessary.

Laboratory parameters will be tabulated as specified in Section 8.2.3.3 in patients whose target disease is painful diabetic neuropathy.

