## 6.3 Concomitant therapy

### (1) Drug therapy

The following information will be entered about all drugs used by the day of safety evaluation. If any adverse event occurs, information will be also entered about the concomitant drugs used during the period from the first day of treatment to the onset of the adverse event. Medications used for treatment of the adverse event should be also recorded.

- [1] Name of drug (brand name)
- [2] Route of administration
- [3] Daily dose
- [4] Number of doses per day

- [5] Dosing period
- [6] Reasons for the use of drugs

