5.4. Subgroups

Subgroup analyses of safety will be performed for the following patient demographics and other factors.

- Hepatic impairment
- Renal impairment
- Children (<15 years), adults (≥ 15 to < 65 years), elderly (≥ 65 years)
- Age [< 65 years, ≥ 65 to < 70 years, ≥ 70 to < 75 years, ≥ 75 to < 80 years, ≥ 80 to < 85 years, ≥ 85 years]
- Sex [male, female]
- Inpatient/outpatient status at the initial prescription [inpatient, outpatient]
- Body weight at the start of treatment (by sex) [< 40 kg, ≥ 40 to < 50 kg, ≥ 50 to < 60 kg, ≥ 60 kg]
- Name of target disease (i.e., diagnosis of neuropathic pain) [by disease name]
- Hemodialysis [no, yes]
- Creatinine clearance [< 15 mL/min, ≥ 15 to < 30 mL/min, ≥ 30 to < 60 mL/min, ≥ 60 mL/min]
- Past medical history [no, yes]
- Complications [no, yes]
- Prior medications [no, yes]
- Concomitant medications [no, yes]
- Non-medication therapies [no, yes]
- Timing of drug administration (at the start of treatment) [before meal, after meal, other]
- Daily dose (at the start of treatment) [≤ 25 mg, > 25 to ≤ 75 mg, > 75 to ≤ 150 mg, > 150 to ≤ 300 mg, > 300 to ≤ 600 mg, > 600 mg]
- Daily dose (maximum) [≤ 25 mg, > 25 to ≤ 75 mg, > 75 to ≤ 150 mg, > 150 to ≤ 300 mg, > 300 to ≤ 600 mg, > 600 mg]
- Pregnant and parturient women (pregnant)

Subgroup analyses of efficacy will be performed for the following patient demographics and other factors.

- Hepatic impairment
- Renal impairment
- Children (<15 years), adults (≥ 15 to < 65 years), elderly (≥ 65 years)
- Age [< 65 years, ≥ 65 to < 70 years, ≥ 70 to < 75 years, ≥ 75 to < 80 years, ≥ 80 to < 85 years, ≥ 85 years]
- Sex [male, female]

- Inpatient/outpatient status at the initial prescription [inpatient, outpatient]
- Body weight at the start of treatment (by sex) [<40 kg, ≥ 40 to <50 kg, ≥ 50 to <60 kg, ≥ 60 kg]
- Name of target disease (i.e., diagnosis of neuropathic pain) [by disease name]
- Hemodialysis [no, yes]
- Creatinine clearance [<15 mL/min, ≥ 15 to <30 mL/min, ≥ 30 to <60 mL/min, ≥ 60 mL/min]
- Past medical history [no, yes]
- Complications [no, yes]
- Prior medications [no, yes]
- Concomitant medications [no, yes]
- Timing of drug administration (at the start of treatment) [before meal, after meal, other]
- Daily dose (at the start of treatment) [≤ 25 mg, >25 to ≤ 75 mg, >75 to ≤ 150 mg, >150 to ≤ 300 mg, >300 to ≤ 600 mg, >600 mg]
- Daily dose (maximum) [≤ 25 mg, >25 to ≤ 75 mg, >75 to ≤ 150 mg, >150 to ≤ 300 mg, >300 to ≤ 600 mg, >600 mg]

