For “peripheral edema and edema-related events”, number and proportion of patients with events will be tabulated by presence or absence of weight increase. Two types of definitions of patients with weight increase are used: 1) those with “weight increased (MedDRA PT)” reported as an adverse reaction; 2) those with body weight increased by 7% or more from baseline at least once. Number and proportion of patients with adverse reactions will be tabulated for each SOC and PT by presence or absence of peripheral edema. In addition, number and proportion of patients with the following adverse reactions will be tabulated by presence or absence of peripheral edema to evaluate the relationship between peripheral edema and cardiovascular and respiratory events.

- Events coded to the MedDRA PT “arrhythmia”, “atrial fibrillation”, “cardiovascular disorder”, “cardiac failure congestive”, “hypertension”, “hypotension”, “palpitations”, “tachycardia”, or “dyspnoea”
- Events coded to the MedDRA SOC “Cardiac disorders”, “Vascular disorders”, or “Respiratory, thoracic and mediastinal disorders”

For “dizziness, somnolence, loss of consciousness, syncope, and potential for accidental injury”, number of days to onset will be tabulated using more specific categories (≤ 4 weeks [1 to 28 days], 1 to 7 days, 8 to 14 days, 15 to 21 days, 22 to 28 days; >4 weeks [≥ 29 days], >4 to ≤ 13 weeks, >13 weeks). In addition, number and proportion of patients with adverse reactions will be tabulated by factor specified in Section 5.4. Tests specified in Section 8.1.3 will be performed to evaluate the relationship between patient demographics, etc. and development of adverse reactions.

Moreover, the median number of days to onset will be tabulated for the following adverse reactions.

- Dizziness
- Somnolence

^a: Occurrence of cardiovascular and respiratory events will be examined in patients with peripheral edema and edema-related events.

- Peripheral edema and edema-related events
- **Pancreas-related events, thyroidal function-related events, change in appetite and activity-related events, suicide-related events, withdrawal symptom and rebound phenomenon-related events, and skin disorder-related events**

Number and proportion of patients will be calculated for each event.

- **Patients with special background**

Number and proportion of patients with adverse reactions and serious adverse reactions will be calculated by SOC and PT in the following subgroups and other patients.

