10.2. Appendix 2: Details of statistical methods

A2.1 Subgroup analysis

Reference populations for calculation of risk ratio and risk difference in subgroup analyses of safety and efficacy are shown below.

Factor	Category	Reference population	Safety/ Efficacy
Special population			
Hepatic impairment	Yes, No	None	Safety, efficacy
Renal impairment	Yes, No	None	Safety, efficacy
Age	Children (<15 years), adults (≥15 to <65 years), elderly (≥65 years)	Adults (≥15 to <65 years)	Safety, efficacy
Patients demographics and others			
Sex	Male, female	Male	Safety, efficacy
Age	<65 years, ≥65 to <70 years, ≥70 to <75 years, ≥75 to <80 years, ≥80 to <85 years, ≥85 years	<65 years	Safety, efficacy
Inpatient/outpatient status at the initial prescription	Inpatient, outpatient	Outpatient	Safety
Body weight (by sex)	<40 kg, ≥40 to <50 kg, ≥50 to <60 kg, ≥60 kg	≥50 to <60 kg	Safety, efficacy
Name of target disease [by disease name]		N/A	N/A
Hemodialysis	Yes, No	None	Safety, efficacy
Creatinine clearance	<15 mL/min, ≥15 to <30 mL/min, ≥30 to <60 mL/min, ≥60 mL/min	≥60 mL/min	Safety, efficacy
Past medical history	Yes, No	None	Safety
Complications	Yes, No	None	Safety
Prior medications	Yes, No	None	Safety, efficacy
Concomitant medications	Yes, No	None	Safety, efficacy
Non-medication therapies	Yes, No	None	Safety
Timing of administration (at the start of treatment)	Before meal, after meal, other	After meal	Safety, efficacy
Daily dose (at the start of treatment)	≤25 mg, >25 to ≤75 mg, >75 to ≤150 mg, >150 to ≤300 mg, >300 to ≤600 mg, >600 mg	>75 to ≤150 mg	Safety, efficacy
Daily dose (maximum)	≤25 mg, >25 to ≤75 mg, >75 to ≤150 mg, >150 to ≤300 mg, >300 to ≤600 mg, >600 mg	>150 to ≤300 mg	Safety, efficacy

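### Safety subgroup factors for concomitant drugs and non-drug therapy have no limit relative to reaction onset, so treatment of a reaction can count as exposure to it

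*SAP*

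**What the plan says.** SAP 5.4 lists the safety subgroup factors. Two of them read "Concomitant medications [no, yes" and "Non-medication therapies [no, yes", with nothing on when the therapy must have been used. Dose and timing of administration in the same list carry a start-of-treatment label. The list is not confined to baseline variables, however, since it also contains "Daily dose (maximum").

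SAP A2.1 introduces its table with "Reference populations for calculation of risk ratio and risk difference in subgroup analyses of safety and efficacy are shown below". For these two factors it adds only that patients without the therapy are the reference.

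The factors are used in two safety comparisons:

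- SAP 8.2.3.4: "Number and proportion of patients with at least one adverse reaction will be tabulated by factor specified in Section 5.4", followed by tests, risk ratios and risk differences with 95% confidence intervals. A significant factor leads to further tables by SOC and PT.
- SAP 8.2.3.1, for the dizziness, somnolence, loss of consciousness, syncope and accidental injury item: "Tests specified in Section 8.1.3 will be performed to evaluate the relationship between patient demographics, etc. and development of adverse reactions".

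On data collection, Protocol 6.3 (1) asks for all drugs used up to the day of safety evaluation and adds "Medications used for treatment of the adverse event should be also recorded". Protocol 6.3 (2) does the same for non-drug therapy. Dates and reasons are collected for both; for drugs the reason field is "Reasons for the use of drugs".

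**The concern.** A subgroup factor meant to explain a reaction should be fixed before the reaction happens. Here it need not be. A patient with no concomitant therapy who has a reaction and is given something for it is recorded as using concomitant therapy. The outcome has then changed the exposure class. This moves reaction cases from the unexposed to the exposed group and raises the risk ratio.

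A second effect can work the other way. Under Protocol 5.4, a patient who stops treatment is followed for only 7 further days. If reactions lead to earlier stopping, reaction patients have less time to start an unrelated therapy than patients observed to Week 13. Any-time use then accumulates more among patients without a reaction, and the risk ratio falls.

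Finding factors that affect safety is a stated objective in SAP 2.2. As written, the risk ratios for these two factors mix any effect of the therapy with what happened after the reaction, and a spurious significant result would trigger further tables.

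**Working it through.** **Is the timing fixed elsewhere?** Four places could settle it, and none does.

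| Place | What it limits | Reaches these comparisons? |
|---|---|---|
| SAP 8.2.3.1, prior and concomitant medications | Drops drugs used after first onset | No. It applies only to the table by PT, target disease and drug class, and never to non-drug therapy |
| SAP 8.2.2, demographics by initial dose | Concomitant drugs at the start of treatment | No. It applies to that demographic table only |
| SAP A1.1 | Data after the safety evaluation date | Only as a cut-off at that date, which is not tied to onset |
| SAP 5.1 and 5.2, separately specified criteria | Inclusion in the analysis sets | No. They do not define factors |

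**Size.** The plan gives no figure on this point, so there is none to reproduce. The documents give neither the share of patients on concomitant therapy nor the share treated for a reaction. Every input below is an assumption.

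- U: share already using the therapy at baseline (drugs 50–85%, non-drug 20–40%)
- p: share with a reaction (20–30%), the same with and without therapy, so the true risk ratio is 1
- t: share of baseline-unexposed reaction patients who become a yes
- o: share of baseline-unexposed patients without a reaction who become a yes

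The four cells, as shares of all patients, are:

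- yes, reaction: p[U + t(1−U)]
- yes, no reaction: (1−p)[U + o(1−U)]
- no, reaction: p(1−U)(1−t)
- no, no reaction: (1−p)(1−U)(1−o)

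The odds ratio is [U + t(1−U)](1−o) / {[U + o(1−U)](1−t)}. Expanding, numerator minus denominator equals t − o. The apparent risk ratio is therefore above 1 when t > o, below 1 when t < o, and exactly 1 when t = o, whatever U and p are.

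*Drugs, base case.* N = 3000, U = 70%, p = 30%. At baseline there are 2100 yes and 900 no, with 630 and 270 reactions.

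| t | o | Reactions/yes | Reactions/no | Risk ratio (95% CI) |
|---|---|---|---|---|
| 2% | 0 | 635/2105 | 265/895 | 1.02 (0.90–1.15) |
| 5% | 0 | 644/2114 | 256/886 | 1.05 (0.93–1.19) |
| 10% | 0 | 657/2127 | 243/873 | 1.11 (0.98–1.26) |
| 30% | 0 | 711/2181 | 189/819 | 1.41 (1.23–1.62) |
| 5% | 10% | 644/2177 | 256/823 | 0.95 (0.84–1.07) |

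For example, at t = 10%, 0.10 × 270 = 27 reaction patients change group: 630 + 27 = 657, 2100 + 27 = 2127, and (657/2127)/(243/873) = 1.11.

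*Non-drug therapy.* N = 3000, U = 20%, p = 30%, t = 5%.

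- o = 0: 216/636 against 684/2364, risk ratio 1.17 (1.04–1.33)
- o = 5%: risk ratio 1.00
- o = 10%: 216/804 against 684/2196, risk ratio 0.86 (0.76–0.98)

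*Ranges over the assumed U and p:*

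| Factor | t | o | Risk ratio |
|---|---|---|---|
| Drugs | 2–5% | 0 | 1.02–1.08 |
| Drugs | 10–30% | 0 | 1.09–1.65 |
| Drugs | 2–30% | 5% | 0.95–1.52 |
| Drugs | 2–30% | 10% | 0.88–1.40 |
| Drugs | 2–30% | 20% | 0.75–1.19 |
| Non-drug | 2–10% | 0 | 1.04–1.41 |
| Non-drug | 2–10% | 2% | 1.00–1.31 |
| Non-drug | 2–10% | 5% | 0.90–1.18 |
| Non-drug | 2–10% | 10% | 0.76–1.00 |

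The risk ratios do not depend on N. At the target of 3400 the intervals would be narrower on the log scale by a factor of √(3000/3400) = 0.94.

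**The case against.** The strongest reply is that this is an unspecified time window and not a demonstrated bias. If few patients are given a drug for a reaction (2–5%), the inflation without offset is only 1.02–1.08. A 10% rate of unrelated starts among patients without a reaction turns it into 0.88–0.96. In the base case the interval includes 1 for 2%, 5% and 10% treated. The larger upward values need treatment rates that nothing in the documents supports. All of this stands, and it is why no net direction is claimed.

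The downward mechanism is also unproven. The 7-day follow-up applies to every early stop, including cure, and the documents do not show that follow-up differs by reaction status. That stands too.

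Protocol 6.3 also asks, when an event occurs, for therapy from the first day of treatment up to onset, and mentions treatment of the event separately. A programmer could therefore derive a pre-onset variable. But the SAP does not tell them to, and 6.3 also records all therapy up to the day of safety evaluation. Two programmers could reasonably build different variables.

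Finally, Protocol 6.9 wants the major items examined by concomitant therapy, and a start-of-treatment definition loses drugs added later but before onset. That is a real cost, taken up under the fix.

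**Conclusion.** The concern holds as a minor point. Followed as written, the tests in SAP 8.2.3.1 for the dizziness and somnolence item, and the tests, risk ratios and risk differences in 8.2.3.4, let the outcome alter the exposure group for these two factors. No other section corrects this.

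The size is not known. It rests on assumed usage, reaction and treatment rates, and the distortion can go either way depending on whether t or o is larger.

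The consequence is limited. SAP 4.1 declares testing exploratory, 4.2 has no decision rule, a significant factor leads only to more tables, and the overall incidence of adverse reactions is unaffected. No bias is shown for the efficacy subgroup analysis in 8.2.4.6.

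**What to change.** For the two safety comparisons named above, define both factors in SAP 5.4 and A2.1 as use at the start of treatment, and state whether therapy first given on Day 1 counts.

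- **Drugs:** use the start-of-treatment variable that SAP 8.2.2 already lists for demographics by initial dose.
- **Non-drug therapy:** derive the equivalent from the period of use collected under Protocol 6.3 (2).
- **Any-time use:** keep it as a descriptive table without a test, risk ratio or risk difference.
- **Efficacy (8.2.4.6):** using the same drug definition is optional, for consistency only.

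The cost is SAP wording, one existing variable and one derived from dates already collected. The loss is therapy begun after baseline but before onset. The drug-class table in 8.2.3.1 covers this only in part: it gives counts by PT, for diseases with about 100 or more patients, and for drugs only.

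A lighter option is to exclude therapies whose recorded reason is treatment of an adverse event. This removes the upward part (t = 0 in the illustration) but not the unequal follow-up. With o of 5–10%, the assumed drug risk ratio would be 0.85–0.96 under a true value of 1.

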### 7.2 Methods of analysis

#### 7.2.1 Safety analysis

In the safety analysis set, the status of onset of adverse reactions and incidence of adverse reactions (percentage of patients developing adverse events for which the causal relationship with the product cannot be ruled out) will be set as primary analysis items. The factors affecting the incidence of adverse reactions will be also analyzed, for example, the incidence of adverse events will be summarized for each of the factors including background variable.

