6.1. Safety endpoints

- Adverse reactions: Adverse events determined to be related to Lyrica by the investigator or the sponsor
- Adverse events: All-causality adverse events
- Serious adverse reactions or adverse events: Adverse reactions or adverse events determined to be serious by the investigator or the sponsor
- Major investigation items:
 - Peripheral edema and edema-related events*
*: Adverse events of the cardiovascular and respiratory systems will also be checked.
 - Dizziness, somnolence, loss of consciousness, syncope, and potential for accidental injury

- Vision-related events

Events to be handled as major investigation items are defined as events of safety specification in the European risk management plan of Lyrica (important identified risk: peripheral edema and edema-related events; dizziness, somnolence, loss of consciousness, syncope, and potential for accidental injury; vision-related events).

- Accident-related events:

Accident-related events are defined as events coded to the MedDRA SMQ “accidents and injuries”. These events will be evaluated for adverse events.

- Pancreas-related events:

Pancreas-related events are defined as events coded to the MedDRA SMQ “acute pancreatitis (narrow scope)”, those coded to the MedDRA HLGT “exocrine pancreas conditions” or the MedDRA HLT “pancreatic neoplasms malignant (excl islet cell and carcinoid)”, and those related to the laboratory test results of primary pancreatic parameters of serum amylase, lipase, and trypsin among those coded to the MedDRA SOC “Investigations”.

- Thyroidal function-related events:

Thyroidal function-related events are defined as events coded to the MedDRA SMQ “thyroid dysfunction”.

- Change in appetite and activity-related events

Change in appetite and activity-related events are defined as events coded to the MedDRA PT “decreased activity”, “decreased appetite”, “increased appetite”, or “hypokinesia”.

- Euphoric mood-related events:

Euphoric mood-related events are defined as events coded to the MedDRA PT “euphoric mood”.

- Suicide-related events:

Suicide-related events are defined as events coded to the MedDRA SMQ “suicide/self-injury”. These events will also be evaluated for adverse events.

- Withdrawal symptom and rebound phenomenon-related events:

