8.2.3.2. Adverse events

- **All adverse events**

Number and proportion of patients with adverse events will be tabulated by SOC and PT.

- **Adverse events by serious/non-serious**

Number and proportion of patients with serious adverse events will be tabulated by SOC and PT. Non-serious adverse events will be tabulated in the same manner.

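### The SAP compares subgroups on adverse reactions only; without the protocol's example of adverse events by factor, a difference in causality attribution cannot be told from a difference in risk

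*SAP*

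**What the plan says.** Protocol 7.2.1 makes adverse reactions the primary safety item, defined as the "percentage of patients developing adverse events for which the causal relationship with the product cannot be ruled out". On factors it says: "The factors affecting the incidence of adverse reactions will be also analyzed, for example", and the example that follows is that "the incidence of adverse events will be summarized for each of the factors including background variable".

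SAP 6.1 separates the two endpoints. Adverse reactions are "Adverse events determined to be related to Lyrica by the investigator or the sponsor"; the other endpoint is "Adverse events: All-causality adverse events".

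SAP 8.2.3.4 sets out the factor analysis: "Number and proportion of patients with at least one adverse reaction will be tabulated by factor specified in Section 5.4". Tests follow, and then "risk ratio and risk difference for the incidence of adverse reactions and their 95% confidence intervals will be calculated between subgroups". The other by-subgroup analyses of events also count adverse reactions:

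- the dizziness, somnolence and accidental injury item by Section 5.4 factor, patients with special background, and dosage and medications (8.2.3.1);
- target disease and initial dose (8.2.3.5).

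For all-causality events, SAP 8.2.3.2 plans: "Number and proportion of patients with adverse events will be tabulated by SOC and PT", and the same split by seriousness. SAP 6.1 also has accident-related and suicide-related events evaluated as adverse events, and the SAP notes that cardiovascular and respiratory adverse events will be checked alongside edema. Section 9 adds listings. None of these is by a Section 5.4 factor.

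**The concern.** SAP 2.2 lists factors considered to affect safety among the survey's objectives. There is no control arm, so comparison between subgroups is the main route to that objective.

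The proportion with an adverse reaction combines two things: how often events occur, and how often they are judged related. Several Section 5.4 factors (age, complications, hemodialysis, renal impairment, concomitant medications) could affect both. A physician who sees dizziness or edema in a patient with other illnesses and other drugs has other explanations at hand, and may link the event to Lyrica less often. An apparent difference could then be one of judgement, and a real excess in a vulnerable group could be hidden.

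Follow-up also depends on the result: SAP 8.2.3.4 produces SOC and PT tables by subgroup for factors that test significant. A masked factor would not trigger that step.

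**Working it through.** **Text comparison.** The protocol's example concerns adverse events by factor. In the SAP, the event analyses by factor or subgroup (8.2.3.1, 8.2.3.4, 8.2.3.5) count adverse reactions. The section on adverse events (8.2.3.2) has no breakdown by factor. The SAP gives no reason for leaving out the example.

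**Inputs.** The plan has no figure of its own on this point. From the documents: a target of 3400 patients and two-sided tests at 5% (SAP 4.1), using Fisher's exact test for nominal factors (SAP 8.1.3). The stated 97% detection probability reproduces (1 − 0.999^3400 = 0.967), but nothing here depends on it. Assumed, because the documents give no values: event incidence, share judged related in each group, and subgroup size.

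**Formula.** P(reaction) = P(event) × P(judged related given event). If P(event) is equal in two groups it cancels, and the reaction risk ratio is the ratio of the two shares, whatever the event rate.

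**Equal risk, unequal attribution.** Take 30% event incidence in both groups, so the true risk ratio is 1.00.

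- 60% judged related in the subgroup, 80% in the reference: 0.30 × 0.60 = 18% v 0.30 × 0.80 = 24%; risk ratio 0.75, difference −6 points.
- 70% v 80%: 0.30 × 0.70 = 21% v 24%; risk ratio 0.88, difference −3 points.

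The chance that Fisher's test gives p < 0.05, summed over the binomial outcomes, depends strongly on subgroup size:

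| Subgroup v rest | 60% v 80% judged related | 70% v 80% judged related |
|---|---|---|
| 510 v 2890 (15% of 3400) | about 86% | about 30% |
| 300 v 3100 | about 66% | about 20% |
| 100 v 3300 | about 25% | about 9% |

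A smaller subgroup gives fewer significant results, but the expected risk ratio is displaced by the same amount.

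**Unequal risk, masked.** Event incidence 40% in the subgroup and 30% in the reference gives a true risk ratio of 1.33. With 60% and 80% judged related, reactions are 0.40 × 0.60 = 24% and 0.30 × 0.80 = 24%: risk ratio 1.00.

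In each case an event column by the same factor would show the underlying 30% v 30%, or 40% v 30%.

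**The case against.** A reader might infer that the SAP drops an analysis the protocol promised. The text does not carry that. The governing clause of Protocol 7.2.1 concerns factors affecting adverse reactions, which are also the primary safety item, and the event summary is introduced as an example. The mixed terms may be loose drafting. SAP 8.2.3.4 delivers the governing clause. What stands is that the example has no counterpart in the SAP and no explanation, so the two texts need reconciling.

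A reader might also infer that the planned comparisons are biased. That is not shown: the documents hold no attribution data by subgroup. Two features may limit the problem. The protocol counts any event whose causal link cannot be ruled out, which is a low threshold, and the SAP counts an event if either the investigator or the sponsor links it. Neither feature removes the judgement, and the two definitions are worded differently.

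All-causality events are no clean remedy. In a single-arm survey their incidence by age, complications or dialysis carries background morbidity unrelated to the drug. This is a good reason to keep adverse reactions primary, and to read the event column beside them rather than in their place.

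Finally, SAP 4.1 calls all testing exploratory, and SAP 8.2.3.5 permits additional analyses. That lowers the stakes. But those analyses are optional and are reported only if they add important interpretation, which is not a commitment to this table.

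**Conclusion.** The point holds as a gap in what the tables can show. All by-factor event analyses rest on a causality judgement, the SAP omits the by-factor event summary that the protocol gives as its example, and the planned output cannot separate attribution from risk. It does not establish that any comparison is biased or that the protocol has been breached.

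The size is conditional. A 60% v 80% difference in attribution displaces the risk ratio to 0.75 under equal risk; 70% v 80% displaces it to 0.88. At 30% event incidence, the chance of a misleading significant result runs from about 9% (70% v 80%, 100 v 3300 patients) to about 86% (60% v 80%, 510 v 2890). The event rate, shares and subgroup sizes are all assumptions. The change is worth making because it is cheap and uses an analysis the protocol itself names.

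**What to change.** Keep adverse reactions as the primary by-factor analysis. Add to SAP 8.2.3.2 or 8.2.3.4 a descriptive column, beside the reaction column, for each Section 5.4 safety factor. It should give the number and proportion of patients with any adverse event, any serious adverse event, and each major investigation item counted as all-causality events. Include risk ratio, risk difference and 95% confidence interval against the A2.1 reference group where one is named.

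Add no significance tests. Five outcomes across the 19 safety factors in Section 5.4 would mean about 5 × 19 = 95 more uncorrected tests at 5%.

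Where the two columns disagree, the report should say so and discuss the factor with both attribution and background morbidity in mind. Do not require both columns to agree before a factor is described as affecting safety. With 36% v 30% true incidence and 60% v 80% attribution, reactions would be 0.36 × 0.60 = 21.6% v 0.30 × 0.80 = 24%, and such a rule would suppress the real excess.

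Cost: SAP wording and more tables, from events already collected and coded. The downside is that all-causality events are less specific to the drug. The SAP's latest version records the survey as completed, so the addition should be labelled as made after data collection.
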